## 3. INTERIM ANALYSIS AND DATA MONITORING COMMITTEE REVIEW

No formal interim analysis is planned for this study. No data monitoring committee is commissioned for this study.

## 4. SUBJECT INFORMATION

The full analysis set and the safety analysis set will be used for the subject information analyses unless otherwise noted. The number of subjects in each analysis set will be summarized by treatment group and overall. In addition, the distribution of subjects by country, and site will be presented.

Simple descriptive statistics, such as mean, median, standard deviation, interquartile range, maximum, and minimum for continuous variables, and counts and percentages for discrete variables will be used to summarize most data and no formal statistical analyses for comparisons of subject information between treatment groups will be performed. In addition, subject listings will also be used to present the data.

### 4.1. Demographics and Baseline Characteristics

#### 4.1.1. Demographics

Table 2 presents a list of the demographic variables that will be summarized by treatment group, and overall for the full analysis set.

Table 2: Demographic Variables	
Continuous Variables:	Summary Type
Age (years)	Descriptive statistics (N, mean, standard deviation [SD], median and range [minimum and maximum], and IQ range).
Weight (kg)	
Height (cm)	
Categorical Variables:	
Age (<45 years, 45 to <65 years, and ≥65 years)	Frequency distribution with the number and percentage of subjects in each category.
Sex (male, female)	
Race a (American Indian or Alaska Native, Asian, Black or African American, Native Hawaiian or other Pacific Islander, White, Other, Multiple)	
Ethnicity (Hispanic or Latino, not Hispanic or Latino)	
BMI (Normal [<25], Overweight [25 -<30], Obese [≥30])	

aIf multiple race categories are indicated, then Race is recorded as “Multiple.”

#### **4.1.2. Baseline Characteristics**

Psoriasis baseline disease characteristics (i.e., psoriasis disease duration [years], age at diagnosis [years], BSA [%], psoriatic arthritis, baseline IGA score, and baseline PASI score [0-72]) will be summarized by treatment group for the full analysis set.

#### **4.2. Disposition Information**

Screened subjects will be summarized overall.

The number of subjects in the following disposition categories will be summarized by treatment group and overall:

- Subjects randomized
- Subjects who received study agent
- Subjects who completed the study
- Subjects who discontinued study agent
- Reasons for discontinuation of study agent
- Subjects who terminated study prematurely
- Reasons for termination of study

The above categories will include summaries over the period of Week 16, Week 20 and Week 40.

Listings of subjects will be provided for the following categories:

- Subjects who discontinued study agent
- Subjects who terminated study prematurely
- Subjects who were unblinded during the study period
- Subjects who were randomized yet did not receive study agent

#### **4.3. Treatment Compliance**

Study agent compliance will be summarized descriptively through Week 20 and Week 28 for the full analysis set. Number of subjects by randomized treatment versus actual treatment will be presented in a summary table.

#### **4.4. Extent of Exposure**

The exposure data will be summarized through Week 20 and through Week 28. The number and percentage of subjects who receive study agent will be summarized by treatment group for the safety analysis set. Descriptive statistics will be presented for the following parameters:

- Number of injections
- Cumulative total dose

In addition, the study agent lots received by treatment, including matching placebo for active treatment will be summarized.

#### **4.5. Protocol Deviations**

In general, the following list of major protocol deviations may have the potential to impact subjects' rights, safety or well-being, or the integrity and/or results of the clinical trial. Subjects with major protocol deviations will be identified prior to database lock and will be summarized by category by treatment group through Week 20 and through Week 40 for the full analysis set.

- Entered but did not satisfy criteria
- Developed withdrawal criteria but not withdrawn
- Received a disallowed concomitant treatment
- Received a wrong treatment or an incorrect dose
- Other

Subjects with major protocol deviations will also be listed by randomized treatment group.

#### **4.6. Prior and Concomitant Medications**

Subjects' prior psoriasis medication history with topical agents, phototherapy, non-biologic systemic therapies, and biologic medications will be summarized by treatment group. See Section 2.4 for lists of medications in each category. In addition, reasons for which subjects discontinued previous systemic therapies (contraindication, inadequate response, intolerance [ie, AEs], or other) will be summarized by randomized treatment group.

The number of subjects who received concomitant treatment with a moisturizer for psoriasis will be summarized by randomized treatment group.

Subjects who received concomitant corticosteroids for indications other than psoriasis and/or psoriatic arthritis will be listed. Subjects with concomitant prophylactic treatments for latent TB infection will also be listed.

### **5. EFFICACY**

In general, efficacy data summaries will be provided by treatment group for the full analysis set.

The Fisher's exact test will be used to compare the proportion of subjects responding to treatment if appropriate. Continuous response parameters (i.e. % improvement in PASI) will be compared using Wilcoxon rank-sum test. All statistical testing will be performed 2-sided.

Descriptive statistics, such as mean, median, standard deviation, minimum and maximum, interquartile range for continuous variables, and counts and percentages for categorical variables will be used to summarize the data. Graphical data displays and subject listings may also be used to summarize the data.

## 5.1. Analysis Specifications

### 5.1.1. Level of Significance

All statistical procedures to test superiority hypotheses will be performed at a 2-sided significance level of 0.05. This study is designed to maintain an overall Type I error of 0.05 or less for the primary analysis and major secondary analyses. Nominal p-values will be reported for other secondary analyses.

#### 5.1.1.1. Multiplicity Adjustment for Testing Procedures

There are 2 co-primary endpoints in this study:

- The proportion of subjects who achieve an IGA score of cleared (0) or minimal (1) at Week 16
- The proportion of subjects who achieve a PASI 90 response at Week 16

Both of the co-primary endpoint analyses will be compared between the guselkumab treatment group and the placebo group and tested at a 2-sided  $\alpha$ -level of 0.05. If one of the comparisons is not significant at the 2-sided  $\alpha$ -level of 0.05, the co-primary endpoints will be considered not significant.

In addition, there are 2 major secondary endpoints in this study to be compared between the guselkumab 100 mg group and the placebo group:

- The proportion of subjects who achieve an IGA score of cleared (0) at Week 16.
- The proportion of subjects who achieve a PASI 100 response at Week 16.

The analyses of the major secondary endpoints will be performed only if both primary analyses are significant, and will be performed in the fixed sequence testing approach, as specified above. If a given comparison is not significant at the 2-sided  $\alpha$ -level of 0.05 for superiority hypotheses, the remaining treatment group comparisons in this sequence will be considered not significant and will be considered as supportive analyses.

### 5.1.2. Definition of the Efficacy Endpoints and Calculation of the Efficacy Instruments

#### 5.1.2.1. Investigator's Global Assessment

The Investigator's Global Assessment (IGA) documents the investigator's assessment of the subject's psoriasis at a given time point. Overall lesions are graded for induration, erythema, and scaling. The patient's psoriasis is assessed as cleared (0), minimal (1), mild (2), moderate (3), or severe (4).

Efficacy endpoints related to the IGA score are defined below:

#### **IGA cleared responder**

Subjects who achieve an IGA score of cleared (0) will be considered IGA cleared responders.

**IGA cleared or minimal responder**

Subjects who achieve an IGA score of cleared (0) or minimal (1) will be considered IGA cleared or minimal responders.

**IGA mild or better responder**

Subjects who achieve an IGA score of cleared (0), minimal (1), or mild (2) will be considered IGA mild or better responders.

**5.1.2.2. Psoriasis Area and Severity Index**

The PASI is a system used for assessing and grading the severity of psoriatic lesions and their response to therapy. In the PASI system, the body is divided into 4 regions: the head, trunk, upper extremities, and lower extremities. Each of these areas is assessed separately for the percentage of the area involved, which translates to a numeric score that ranges from 0 (indicates no involvement) to 6 (90%-100% involvement), and for erythema, induration, and scaling, which are each rated on a scale of 0 to 4. The PASI produces a numeric score that can range from 0 (no psoriasis) to 72. A higher score indicates more severe disease.

Efficacy endpoints related to the PASI score are defined below:

**PASI 50 Responder**

Subjects with  $\geq 50\%$  improvement in PASI from baseline will be considered PASI 50 responders.

**PASI 75 Responder**

Subjects with  $\geq 75\%$  improvement in PASI from baseline will be considered PASI 75 responders.

**PASI 90 Responder**

Subjects with  $\geq 90\%$  improvement in PASI from baseline will be considered PASI 90 responders.

**PASI 100 Responder**

Subjects with 100% improvement in PASI from baseline (PASI score=0) will be considered PASI 100 responders.

**5.1.3. Data Handling Rules**

The following treatment failure rules and data handling rules will be applied to the PASI and IGA-related efficacy analyses in this study.

**5.1.3.1. Treatment Failure Criteria**

Subjects who discontinue study agent due to lack of efficacy, an adverse event (AE) of worsening of psoriasis, or who started a protocol-prohibited medication/therapy during the study that could affect their psoriasis are considered as treatment failures.

The particular protocol-prohibited medications/therapies include:

**Topical Therapies:**

- Any topical therapies used for psoriasis (with the exception of topical moisturizers and shampoos containing tar or salicylic acid only)

**Phototherapy or Systemic Therapies:**

- Any systemic corticosteroid used for psoriatic arthritis or psoriasis with the exception of intra-articular corticosteroids.
- Any other anti-psoriatic systemic therapy or biologic therapy.
- Phototherapy of UVB or PUVA.
- Any other phototherapy for psoriasis.

**5.1.3.2. Treatment Failure Rules**

A subject who meets one or more treatment failure criterion specified in Section 5.1.3.1 will be considered a treatment failure from that point onward. The baseline values will be used for all directly measured endpoints regardless of the actual measurements. Zero will be assigned to improvement and percent improvement, and non-responder status will be assigned to binary response variables.

Treatment failure is assumed to have occurred at the earlier of the following dates:

- Date of discontinuation (DC) of study treatment due to lack of efficacy or
- Date of discontinuation of study agent due to an AE of worsening of psoriasis or
- Start date of a protocol-prohibited medication/therapy during the study that could improve psoriasis

**5.1.3.3. Missing Data Imputation**

After the treatment failure rules are applied, the remaining missing data will be handled as follows for all of the efficacy analyses including the analyses at the key visit (Week 16) and over time:

- Non-responder imputation will be applied for binary endpoints.
- No imputation will be performed for continuous endpoints and the values will remain as missing.

**5.2. Primary Efficacy Endpoint(s)****5.2.1. Definition**

There are 2 co-primary endpoints in this study: the proportion of subjects who achieve an IGA score of cleared (0) or minimal (1) at Week 16 and the proportion of subjects who achieve a PASI 90 response at Week 16. Refer to Section 5.1.2.1 and 5.1.2.2 for the definition of IGA score and PASI 90 responder.

### 5.2.2. Estimand

**Population:** subjects with moderate-to-severe plaque psoriasis who are randomized and treated with guselkumab or placebo using the SelfDose device.

**Endpoint:** the proportion of subjects who achieve an IGA score of cleared (0) or minimal (1) at Week 16 and the proportion of subjects who achieve a PASI 90 response at Week 16

**Measure of Intervention:** the effect of the initially randomized treatment regardless of what treatments are actually received. Non-responder status will be assigned if treatment failure criteria are met or data are missing.

### 5.2.3. Analysis Methods

These 2 co-primary endpoints will be compared between the guselkumab 100 mg group and the placebo group. In these primary efficacy analyses, data from all randomized and treated subjects will be analyzed according to their assigned treatment group. The number and proportion of subjects who achieve an IGA score of cleared (0) or minimal (1) and PASI 90 response at Week 16 will be summarized for each treatment group respectively. The differences in proportions with exact 95% confidence intervals will also be presented.

To address the primary objective, a 2-sided ( $\alpha=0.05$ ) Fisher's exact test will be used for the co-primary endpoints.

The study will be considered positive if the guselkumab 100 mg group is significantly different from the placebo group for both co-primary endpoints. Both co-primary endpoints will be tested at a 2-sided  $\alpha$ -level of 0.05. If one of the comparisons is not significant, the co-primary endpoints will be considered not significant.

### 5.2.4. Data Handling

Subjects who meet treatment failure criteria specified in Section 5.1.3.1 prior to Week 16 will be considered not to have achieved an IGA score of cleared (0) or minimal (1) or PASI 90 at Week 16. In addition, subjects with a missing IGA or PASI score at Week 16 or who do not return for evaluation at Week 16 will be considered not to have achieved the respective endpoint at Week 16.

### 5.2.5. Sensitivity Analysis

To assess the robustness of the co-primary endpoint analysis results, two sensitivity analyses will be conducted in the same manner as the co-primary endpoints. The missing data will be handled as specified below.

#### Sensitivity Analysis 1

For subjects who do not return for evaluation at Week 16, the missing IGA or PASI score at Week 16 will not be imputed. That is, the analysis will be performed using observed data after applying treatment failure rules (as defined in Section 5.1.3.2).

## Sensitivity Analysis 2

The second sensitivity analysis will be performed by using multiple imputations (MI). In this analysis, for subjects who meet one or more treatment failure criterion specified in Section 5.1.3.1, the IGA and PASI score will be treated as missing from that point onward. The missing IGA or PASI score will be imputed using the Markov Chain Monte Carlo (MCMC) algorithm which assumes that all the variables in the imputation model have a joint multivariate normal distribution. The IGA or PASI responses will then be derived based on the imputed score at Week 16.

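### Sensitivity Analysis 2 imputes a 0–4 IGA grade and a skewed, zero-bounded PASI from a joint normal, gives no IGA cut-off for a non-integer draw, and has no way to combine Fisher's test and exact intervals across imputations

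*SAP*

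**What the plan says.** SAP Section 5.2.5 plans two sensitivity analyses for the co-primary endpoints. In the second, scores after treatment failure are set to missing. These and other missing scores are imputed by MCMC, "which assumes that all the variables in the imputation model have a joint multivariate normal distribution". Then: "The IGA or PASI responses will then be derived based on the imputed score at Week 16".

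The scales and responder rules are in Section 5.1.2:

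- IGA has five whole grades, 0 to 4. "Subjects who achieve an IGA score of cleared (0) or minimal (1) will be considered IGA cleared or minimal responders".
- "The PASI produces a numeric score that can range from 0 (no psoriasis) to 72". Subjects with at least 90% "improvement in PASI from baseline will be considered PASI 90 responders".

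On how the imputed data are analysed, Section 5.2.5 says only that "two sensitivity analyses will be conducted in the same manner as the co-primary endpoints". Section 5.2.3 defines that manner as a two-sided Fisher's exact test at 0.05, and adds: "The differences in proportions with exact 95% confidence intervals will also be presented".

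**The concern.** There are three gaps.

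1. **IGA cut-off.** A normal draw is almost never a whole number. The responder rule covers grades 0 and 1 and does not classify 1.3 or 1.7. The SAP gives no rounding, bounding or threshold, so programmers following the same text can report different response rates.
2. **PASI shape.** The PASI 90 rule can be applied to a continuous draw, so nothing is ambiguous. The difficulty is fit. On an effective treatment, PASI scores pile up at and just above zero with a long right tail, and the PASI 90 threshold lies in that region, where a normal curve describes the data worst.
3. **No single result.** Rubin's rules need an estimate and a variance from each imputed data set. Fisher's test yields only a p-value, and an exact interval supplies no standard error. As written, the analysis ends with one p-value and one interval per imputation.

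This is the only model-based imputation check on the co-primary results, and the only one that relaxes the treatment-failure rule. Section 1.5.2 unblinds most of the sponsor at the Week 20 lock, so choices left open could be settled with results in view.

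**Working it through.** **Inputs from the SAP (Section 1.4).** 60 guselkumab and 15 placebo subjects; placebo rates 10% (IGA 0/1) and 5% (PASI 90); guselkumab rates 86% and 62%. The SAP's power table reproduces with exact Fisher power: 99.7%, 99.9% and >99.9% for IGA 0/1 at 70, 75 and 80%; 98.7%, 99.7% and 99.9% for PASI 90 at 55, 60 and 65%. The point does not depend on that table.

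**Assumptions.** The SAP gives no score distributions and no missing-data rate. Those below are assumed, with ranges.

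**Step 1: IGA.** For an assumed grade distribution with mean m and SD s, the imputed response is Φ((c − m)/s), where c is the cut-off. Example, 50/34/10/5/1% in grades 0 to 4: m = 0.34 + 0.20 + 0.15 + 0.04 = 0.73; mean square = 0.34 + 0.40 + 0.45 + 0.16 = 1.35; s = √(1.35 − 0.73²) = 0.904. At c = 1, Φ(0.27/0.904) = 61.7%.

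| Grades 0/1/2/3/4 (%) | True 0/1 | Draw ≤1 | Rounded (<1.5) | Draw <2 |
|---|---|---|---|---|
| 50/34/10/5/1 | 84 | 61.7 | 80.3 | 92.0 |
| 45/41/9/4/1 | 86 | 61.5 | 81.0 | 92.9 |
| 60/26/8/5/1 | 86 | 66.7 | 83.7 | 93.8 |
| 30/54/10/5/1 | 84 | 53.4 | 75.4 | 90.2 |

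Whole-arm shift = imputed share × (imputed rate − true rate). With 5–15% imputed:

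- draw ≤1: from 0.05 × (66.7 − 86) = −1.0 to 0.15 × (53.4 − 84) = −4.6 points;
- rounded: −0.1 to −1.3 points;
- draw <2: +0.3 to +1.2 points.

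**Step 2: PASI 90.** Nine assumed guselkumab distributions were used: baseline 12 plus a gamma variable (shape 1.6, scale 6); 30, 35 or 40% of subjects at PASI 0; the rest a lognormal fraction of baseline with log-SD 0.8, 1.0 or 1.3; all set to 62% PASI 90. A normal draw conditional on baseline, counted as a response when it is at most 10% of baseline, gives about 41–49%. The whole-arm shift with 5–15% imputed runs from 0.05 × (49 − 62) = −0.7 to 0.15 × (41 − 62) ≈ −3.2 points.

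**Step 3: does it matter who is imputed?** Steps 1 and 2 assume that imputed subjects resemble the whole arm. In simulated trials with 6 of 60 and 2 of 15 scores deleted at random, response among imputed guselkumab subjects was:

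- IGA: 63.0% (≤1), 79.7% (rounded), 90.4% (<2), 84.2% (predictive mean matching); truth 83.4%.
- PASI 90: 49.0% (normal), 62.3% (matching); truth 61.8%.

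When the guselkumab subjects worst at the previous visit were deleted instead, as a stand-in for treatment failures, two separate IGA runs gave truth 45%, rounding 37%, matching 51%; and truth 42%, rounding 36%, matching 44%. In the second run, restricting donors to the same arm gave 57%.

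**Step 4: pooling with 15 placebo subjects.** The probability of no placebo responder is 0.95^15 = 46% (PASI 90) and 0.90^15 = 21% (IGA 0/1). The usual standard error of that arm is then 0. With one success and one failure added it is √((1/17)(16/17)/17) = 0.057.

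The added-count interval is centred as follows at the planning rates:

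- IGA: (51.6 + 1)/62 − (1.5 + 1)/17 = 70.1 points, against 76.0 unadjusted.
- PASI 90: (37.2 + 1)/62 − (0.75 + 1)/17 = 51.3 points, against 57.0 unadjusted.

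Enumerating all 61 × 16 = 976 complete-data outcomes, it contains the unadjusted difference every time. Test size is 0.5, 1.4, 3.7, 4.9 and 5.6% at common rates of 5, 10, 20, 30 and 50%, and 5.6% is the maximum. The ordinary Wald test reaches about 21%.

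**Step 5: could the conclusion move?** Fisher's p is 1.3 × 10⁻⁷ for 52/60 against 2/15, 1.0 × 10⁻⁵ for 46/60 against 2/15, and 0.0009 for 33/60 against 1/15. In 300 simulated trials (IGA, rounded), none had imputations on both sides of 0.05.

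**The case against.** The strongest reply is that little hangs on this analysis. The primary analysis uses non-responder imputation, Sensitivity Analysis 1 uses observed data, and Sensitivity Analysis 2 lies outside the testing hierarchy of Section 5.1.1.1. With rounding, the arm moves by about a point at most. All of that stands, and it limits the weight of the point. It does not make the stated test yield one result.

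Four further objections have force:

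- **Negative PASI draws.** A reader might infer that draws below zero, roughly a quarter to a third under the assumed distributions, are errors in themselves. They are not: a negative draw is a PASI 90 responder, just as 0 is. They signal poor fit; the harm is the under-count at the threshold, and its size rests on assumed distributions.
- **The <2 cut-off.** Truncating down is the least natural reading, and without it both remaining IGA choices under-count guselkumab response. They still differ by 17 to 22 points per imputed subject in the table above.
- **Matching.** A reader might infer from the random-deletion runs that matching is unbiased. When the imputed subjects are mainly poor responders it is closer to the truth than rounding, but not unbiased.
- **Early failures.** A subject who fails before Week 16 also lacks the intermediate scores. The joint normal model copes with that pattern, so any replacement must too.

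**Conclusion.** The point holds as a should-fix item on a supportive analysis. Section 5.2.5 leaves the IGA responder rule open for non-integer draws. It uses a model that, under the assumed skewed distributions, gives too few guselkumab PASI 90 responders, and it prescribes a test and interval that cannot be combined into one result.

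For imputed subjects the choice of IGA cut-off moves response from 53–67% to 90–94%, and PASI 90 falls to about 41–49% against 62%. For the whole arm this is at most about 4.6 points (IGA) or 3.2 points (PASI 90) with 5–15% imputed. Distributions and missing rates are assumptions, and the figures treat imputed subjects as typical of their arm; if they are mainly treatment failures, their true response is lower.

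A reader might infer that the primary result or the Type I error is at risk. The SAP does not support that: Sections 5.1.3.3 and 5.2.4 fix the primary handling as non-responder imputation, independent of this analysis, and at the planned effect the conclusion is unlikely to change.

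**What to change.** In Section 5.2.5, replace the imputation and response sentences for Sensitivity Analysis 2 with text to this effect:

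- Use fully conditional imputation in visit order, so that subjects who fail or drop out before Week 16 have their intermediate scores imputed first.
- For IGA, use an ordinal model or predictive mean matching on grades 0–4. For PASI, use predictive mean matching on percent improvement. Fit each as a separate main-effects model with arm, baseline and earlier scores, with donors from both arms.
- Derive response by Section 5.1.2. Fix the number of imputations and the seed before the Week 20 database lock.
- In this analysis only, replace Fisher's test and the exact interval by the difference in proportions pooled by Rubin's rules, with the interval and p-value computed after adding one success and one failure to each arm.

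Minimum acceptable alternative: keep the normal model, state that IGA is rounded to the nearest grade (response if the draw is below 1.5), and state the same pooling rule. This leaves the PASI under-count in place.

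Optional: report the added-count interval once on the primary data, and add a version that keeps failures as non-responders.

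The cost is SAP wording and modest programming, with no new data. The interval is approximate and is centred about 6 points below the reported estimate. Placebo donors are few, so the models must stay simple.
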